92 PRIVILEGED AND CONFIDENTIAL COMMUNICATION

			Norn	nal	Grade	e 1	Grad	le 2	Grad	le 3	Grad	e 4
a meter	Study Day	N	u	%	n	0∕∕0	u	%	n	%₀	n	%
	Max Post Baseline											

Note: The "Max Post Baseline" row includes the maximum severity experienced by each subject at any time point post baseline, including unscheduled assessments.

Tables with similar format:

- Distribution of Laboratory Results (Ordinal-Graded) by Parameter, Severity, Study Day, and Study Group Part A, Group 2 Table 112:
  - Distribution of Laboratory Results (Ordinal-Graded) by Parameter, Severity, Study Day, and Study Group Part A, Group 3 Table 113:
- Distribution of Laboratory Results (Binary-Graded) by Parameter, Severity, Study Day, and Study Group Part B Table 114:
- Distribution of Laboratory Results (Ordinal-Graded) by Parameter, Severity, Study Day, and Study Group Part B, Group 4 Table 115:
- Distribution of Laboratory Results (Ordinal-Graded) by Parameter, Severity, Study Day, and Study Group Part B, Group 5 Table 116:
- Laboratory Summary Statistics by Parameter, Study Day, and Study Group Part A, Group 1 Table 117:

Laboratory Parameter	Statistic	Baseline	Day 28 (Visit 03)	Day 42 (Visit 03B)	Day 56 (Visit 04)	Day 70 (Visit 04B)	Day 84 (Visit 05)	Day 112 (Visit 06)
[Parameter 1]	Z	х						
	Mean	X.XX						
	Standard Deviation	X.XX						
	Median	X'XX						

Day 112 (Visit 06)																
Day 84 (Visit 05)																
Day 70 (Visit 04B)																
Day 56 (Visit 04)																
Day 42 (Visit 03B)																
Day 28 (Visit 03)																
Baseline	XX.X, XX.X	N/A	N/A	N/A	N/A	N/A	х	X.XX	X.XX	X.XX	XX.X, XX.X	N/A	N/A	N/A	N/A	N/A
Statistic	Min, Max	Ν	Mean	Standard Deviation	Median	Min, Max	Ν	Mean	Standard Deviation	Median	Min, Max	Ν	Mean	Standard Deviation	Median	Min, Max
Laboratory Parameter		[Parameter 1 Change from Baseline]					[Parameter 2]					[Parameter 2 Change from Baseline]				

Implementation Note: If the number of Study Groups or assessment time points causes this table to be too wide (wider than the page), then split this table by Study Group (i.e., one table per Study Group).

If there are a lot of hematology and biochemistry values, or if the time points differ for the two sets of parameters, then split this table into separate hematology and biochemistry tables. A separate table will also likely be needed for urinalysis.

Include change from baseline for each test as a Laboratory Parameter. See example below.

For calculated fields (Mean, SD, Median), decimal place should be the format in which the data were collected + 1 extra place. For Min, Max, decimal place should be in the same format in which the data were collected.]

Tables with similar format:

Laboratory Summary Statistics by Parameter, Study Day, and Study Group – Part A, Group 2 Table 118:

Laboratory Summary Statistics by Parameter, Study Day, and Study Group – Part A, Group 3 Table 119:

ated fields (Mean, SD, Median	), decimal place s	hould be the	format in whi	ch the data w	ere collected	+ 1 extra plae
, decimal place should be in the	e same format in v	which the dat	a were collect	ced.]		
Lahoratory Parameter	Statistic	Baseline	Day 28 (Visit 03)	Day 56 (Visit 04)	Day 112 (Visit 06)	Day 308 (Visit 13)
[Parameter 1]	Z	x				
	Mean	X.XX				
	Standard Deviation	XX.X				
	Median	XX.X				
	Min, Max	XX.X, XX.X				
[Parameter 1 Change from Baseline]	Ν	N/A				
	Mean	N/A				
	Standard Deviation	N/A				
	Median	N/A				
	Min, Max	N/A				
[Parameter 2]	N	х				
	Mean	XX.X				
	Standard Deviation	XX.X				
	Median	XX.X				
	Min, Max	XX.X, XX.X				
[Parameter 2 Change from Baseline]	Ν	N/A				
	Mean	N/A				

tra place. For For calcula Min, Max.

Statistical Analysis Plan - VRC Protocol 705

[Implementation Note: If the number of Study Groups or assessment time points causes this table to be too wide (wider than the page),

then split this table by Study Group (i.e., one table per Study Group).

If there are a lot of hematology and biochemistry values, or if the time points differ for the two sets of parameters, then split this table into separate hematology and biochemistry tables. A separate table will also likely be needed for urinalysis.

Include change from baseline for each test as a Laboratory Parameter. See example below.

96

PRIVILEGED AND CONFIDENTIAL COMMUNICATION

11NOV2019 Version 1.0

Standard Deviation	N/A		
Median	N/A		
Min, Max	N/A		

Table with a similar format:

 Table 121:
 Laboratory Summary Statistics by Parameter, Study Day, and Study Group – Part B, Group 5
# Table 122: Shift Table for RBC by Study Group Comparing Baseline to Post-Baseline Measures – Part A

	Group DN 2	1: 4 mg ZIK A, 2 injection Baseline	Vwt s	Group DN.	2: 4 mg ZIK A, 4 injection Baseline	Vwt Is	Group 3: 8 4	8 mg ZIKVwt injections Baseline	t DNA,
	Normal	Abnormal	Total	Normal	Abnormal	Total	Normal	Abnormal	Total
Post Baseli	ne Week	4 (Visit 03)							
Normal									
Abnormal									
Total									
Post Baseli	ine Week (	6 (Visit 03B)							
Normal									
Abnormal									
Total									
Post Baseli	ine Week	8 (Visit 04)							
Normal									
Abnormal									
Total									
Post Baseli	ine Week	10 (Visit 04B)	(						
Normal									
Abnormal									
Total									
Post Baseli	ine Week	12 (Visit 05)							
Normal									
Abnormal									
Total									
Post Baseli	ne Week	16 (Visit 06)							

	Group DN2	1: 4 mg ZIK A, 2 injection Baseline	Vwt s	Group DN	2: 4 mg ZIK A, 4 injection Baseline	Vwt Is	Group 3: 8 4	8 mg ZIKVw injections Baseline	t DNA,
	Normal	Abnormal	Total	Normal	Abnormal	Total	Normal	Abnormal	Total
Normal									
Abnormal									
Total									

Tables with a similar format:

Shift Table for Hematocrit by Study Group Comparing Baseline to Post-Baseline Measures – Part A Table 123:

Shift Table for MCV by Study Group Comparing Baseline to Post-Baseline Measures – Part A Table 124:

Shift Table for Monocytes by Study Group Comparing Baseline to Post-Baseline Measures – Part A Table 125:

Shift Table for Basophils by Study Group Comparing Baseline to Post-Baseline Measures – Part A Table 126:

Shift Table for ALT by Study Group Comparing Baseline to Post-Baseline Measures – Part A, Group 1 Table 127:

			Base	line		
	Normal	Grade 1	Grade 2	Grade 3	Grade 4	Total
Post Base	line Week	4 (Visit 03)				
Normal	х	х	х	х	х	х
Grade 1	Х	х	х	х	Х	Х
Grade 2	х	х	х	х	х	х
Grade 3	Х	х	х	х	х	Х
Grade 4	х	х	х	х	х	х
Total	х	х	х	х	х	X
Post Basel	ine Week 6	(Visit 03B)				
Normal	x	x	х	х	x	x
Grade 1	х	х	х	х	х	Х
Grade 2	х	х	х	х	х	х
Grade 3	Х	х	х	х	Х	Х
Grade 4	х	х	х	х	х	х
Total	х	х	х	х	х	Х
Post Basel	ine Week 8	(Visit 04)				
Normal	Х	х	х	х	х	Х
Grade 1	Х	х	х	х	х	Х
Grade 2	Х	х	х	х	х	Х
Grade 3	х	х	х	х	х	х
Grade 4	Х	х	х	х	Х	х

100 PRIVILEGED AND CONFIDENTIAL COMMUNICATION

			4	:		
			Base	eline		
	Normal	Grade 1	Grade 2	Grade 3	Grade 4	Total
Total	Х	Х	Х	х	Х	Х
Post Basel	ine Week I	0 (Visit 04H	3)			
Normal	Х	х	Х	х	Х	Х
Grade 1	x	х	х	Х	х	х
Grade 2	x	х	х	Х	х	х
Grade 3	x	x	x	x	x	х
Grade 4	x	х	х	х	х	Х
Total	x	x	x	x	x	х
Post Basel	ine Week I.	2 (Visit 05)				
Normal	x	x	x	х	x	х
Grade 1	x	x	х	х	х	х
Grade 2	x	х	х	х	х	Х
Grade 3	х	х	х	х	х	Х
Grade 4	x	x	х	х	х	х
Total	х	х	х	х	х	Х
Post Basel	ine Week I	6 (Visit 06)				
Normal	Х	х	Х	х	Х	Х
Grade 1	Х	Х	Х	х	Х	Х
Grade 2	Х	х	Х	х	х	Х
Grade 3	Х	х	х	х	х	х
Grade 4	Х	х	Х	х	х	Х
Total	x	Х	х	X	Х	Х

101 PRIVILEGED AND CONFIDENTIAL COMMUNICATION

Tables with similar format:

Table 128:	Shift Table for ALT by Study Group Comparing Baseline to Post-Baseline Measures – Part A, Group 2
Table 129:	Shift Table for ALT by Study Group Comparing Baseline to Post-Baseline Measures – Part A, Group 3
Table 130:	Shift Table for WBC by Study Group Comparing Baseline to Post-Baseline Measures – Part A, Group 1
Table 131:	Shift Table for WBC by Study Group Comparing Baseline to Post-Baseline Measures – Part A, Group 2
Table 132:	Shift Table for WBC by Study Group Comparing Baseline to Post-Baseline Measures – Part A, Group 3
Table 133:	Shift Table for Hemoglobin by Study Group Comparing Baseline to Post-Baseline Measures – Part A, Group 1
Table 134:	Shift Table for Hemoglobin by Study Group Comparing Baseline to Post-Baseline Measures – Part A, Group 2
Table 135:	Shift Table for Hemoglobin by Study Group Comparing Baseline to Post-Baseline Measures – Part A, Group 3
Table 136:	Shift Table for Platelets by Study Group Comparing Baseline to Post-Baseline Measures – Part A, Group 1
Table 137:	Shift Table for Platelets by Study Group Comparing Baseline to Post-Baseline Measures – Part A, Group 2
Table 138:	Shift Table for Platelets by Study Group Comparing Baseline to Post-Baseline Measures – Part A, Group 3
Table 139:	Shift Table for Neutrophils by Study Group Comparing Baseline to Post-Baseline Measures – Part A, Group 1
Table 140:	Shift Table for Neutrophils by Study Group Comparing Baseline to Post-Baseline Measures – Part A, Group 2
Table 141:	Shift Table for Neutrophils by Study Group Comparing Baseline to Post-Baseline Measures – Part A, Group 3
Table 142:	Shift Table for Lymphocytes by Study Group Comparing Baseline to Post-Baseline Measures – Part A, Group 1
Table 143:	Shift Table for Lymphocytes by Study Group Comparing Baseline to Post-Baseline Measures – Part A, Group 2
Table 144:	Shift Table for Lymphocytes by Study Group Comparing Baseline to Post-Baseline Measures – Part A, Group 3
Table 145:	Shift Table for Eosinophils by Study Group Comparing Baseline to Post-Baseline Measures – Part A, Group 1
Table 146:	Shift Table for Eosinophils by Study Group Comparing Baseline to Post-Baseline Measures – Part A, Group 2
Table 147:	Shift Table for Eosinophils by Study Group Comparing Baseline to Post-Baseline Measures – Part A, Group 3

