# 8.6. Risks and Benefits

# 8.6.1. Risks of the ZIKVwt DNA vaccine

The investigational ZIKV DNA vaccine, VRC-ZKADNA085-00-VP, which is similar to the ZIKVwt DNA vaccine, VRC-ZKADNA090-00-VP, is being tested in a Phase 1 study, VRC 319. As of July 24, 2018, 80 subjects have enrolled into VRC 319 and received at least 2 or 3 injections of the ZIKV DNA vaccine by needle and syringe; 45 subjects have enrolled into VRC 320 and received at least one injection of the ZIKVwt DNA vaccine by PharmaJet. Both products have been well tolerated based on early findings, as reported in Section 1.3.

Subjects may exhibit general signs and symptoms associated with administration of a vaccine including fever, chills, rash, aches and pains, nausea, headache, dizziness and fatigue. These

side effects will be monitored, but are generally short term, mild to moderate in severity and usually do not require treatment.

In previous VRC DNA vaccine studies, placebo and vaccine recipients were noted to have occasional asymptomatic and self-limited changes in laboratory tests such as temporary decrease in white blood cell count. Urticaria has been reported as an AE possibly related to DNA vaccines.

Neurological complications including GBS have been reported in people diagnosed with ZIKV infection. While GBS has not been observed with other DNA vaccines or vaccines developed against other flaviviruses, we cannot rule out all concern for GBS. The cause of GBS associated with ZIKV disease is still under investigation. To minimize the risk of GBS, which has been shown to increase with age, the study population is limited to healthy adults and adolescents 15-35 years of age.

It is unknown if the study vaccine will affect how subjects respond to a future ZIKV infection or ZIKV vaccine that may be available in the future. There may be side effects from the study products, which may be serious or life threatening, that we do not yet know about.

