\* The laboratory values provided in the tables serve as guidelines and are dependent upon institutional normal parameters. Institutional normal reference ranges should be provided to demonstrate that they are appropriate. \*\* The clinical signs or symptoms associated with laboratory abnormalities might result in characterization of the laboratory abnormalities as Potentially Life Threatening (Grade 4). For example, a low sodium value that falls within a grade 3 parameter (125-129 mE/L) should be recorded as a grade 4 hyponatremia event if the subject had a new seizure associated with the low sodium value.

\*\*\* "ULN" is the upper limit of the normal range.

Hematology*	Mild (Grade 1)	Moderate (Grade 2)	Severe (Grade 3)	Potentially Life Threatening (Grade 4)
Hemoglobin (Female) - gm/dL	11.0 - 12.0	9.5 - 10.9	8.0 - 9.4	< 8.0
Hemoglobin (Female) decrease from baseline value - gm/dL	not applicable	1.6 – 2.0	2.1 – 5.0	> 5.0
Hemoglobin (Male) - gm/dL	12.5 – 13.5	10.5 - 12.4	8.5 - 10.4	< 8.5
Hemoglobin (Male) decrease from baseline value – gm/dL	not applicable	1.6 – 2.0	2.1 – 5.0	> 5.0
WBC Increase - cell/mm 	10,800 - 15,000	15,001 - 20,000	20,001 - 25,000	> 25,000
WBC Decrease - cell/mm 	2,500 - 3,500	1,500 - 2,499	1,000 - 1,499	< 1,000
Lymphocytes Decrease - cell/mm 	750 – 1,000	500 - 749	250 - 499	< 250
Neutrophils Decrease - cell/mm 	1,500 - 2,000	1,000 - 1,499	500 - 999	< 500
Eosinophils - cell/mm 	650 - 1500	1501 - 5000	> 5000	Hypereosinophilic
Platelets Decreased - cell/mm 	125,000 - 140,000	100,000 - 124,000	25,000 - 99,000	< 25,000
PT – increase by factor (prothrombin time)	1.10 x ULN**	1.11 – 1.20 x ULN	1.21 – 1.25 x ULN	>1.25 ULN
PTT – increase by factor (partial thromboplastin time)	1.10 – 1.20 x ULN	1.21 – 1.4 x ULN	1.41 – 1.5 x ULN	> 1.5 x ULN
Fibrinogen increase - mg/dL	400 - 500	501 - 600	> 600	
Fibrinogen decrease - mg/dL	150 - 200	125 – 149	100 - 124	< 100 or associated with gross bleeding or disseminated intravascular coagulation (DIC)

\* The laboratory values provided in the tables serve as guidelines and are dependent upon institutional normal parameters. Institutional normal reference ranges should be provided to demonstrate that they are appropriate.

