# 2) For laboratory parameters with three categories: Low, Normal and High (Ordinal response)

- a. For each parameter the shift table displays the number of subjects who are categorized as low, normal, or high at baseline cross tabulated with low, normal or high results at the post-vaccination visit.
- b. A GEE model for the ordinal responses above is fitted and used for parameter estimation
  - Observation  $(Y_{ij}, X_{ij})$  for each subject i = 1, ..., n at time point j = 1, ..., J.  $Y_{ij} = (y_{ij1}, y_{ij2})$  is the ordinal response variable with 3 ordered categories;
  - Cumulative probability pijk = Pr(yijk = 1: in lower k category) = Pr(Yij ≤ k), k = 1,2;
  - Proportional Odds model  $\begin{cases} g(p_{ij1}) = \mu_1 + X'_{ij}\beta \\ g(p_{ij2}) = \mu_2 + X'_{ij}\beta \end{cases}$  using the logit link;
  - $X'_{ij}\beta = -\beta_1 t_{ij} + \beta_2 group_{ij} + \beta_3 t_{ij} * group_{ij}$
  - GEE:  $\sum_{i=1}^{n} \left(\frac{\partial P_i}{\partial \beta}\right) V_i^{-1}(\alpha) (Y_i P_i) = 0$  where  $P_i = E(Y_i) V_i(\alpha)$  is the working covariance matrix;
  - Output: estimates of two intercepts from the two fitted logistic models; point estimates and 95% CI for the individual levels of the GROUP, TIME and GROUP\*TIME variables, and Type-3 SAS output for the parameter significance (chi-Square test);

The study is not powered to detect differences by study group, therefore the absence of statistically significant differences should not be interpreted as no such differences exist.

Individual clinical laboratory results will be presented for subjects with abnormal results of Grade 2 or higher for at least one parameter from at least one visit, including planned parameters collected at scheduled visits as well as any other parameters collected, and any results for unscheduled visits in Table 167 for **Part A** and Table 168 for **Part B**, **Appendix 1**.

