- Distribution of Abnormal Laboratory Results (Ordinal-Graded) Related to Study Treatment by Parameter, Severity, Study Day, and Study Group - Part A, Group 3 Table 171:
- Distribution of Abnormal Laboratory Results (Ordinal-Graded) Related to Study Treatment by Parameter, Severity, Study Day, and Study Group - Part B, Group 4 Table 172:
- Distribution of Abnormal Laboratory Results (Ordinal-Graded) Related to Study Treatment by Parameter, Severity, Study Day, and Study Group – Part B, Group 5 Table 173:

## Table 174: Distribution of Vital Signs by Day Post Dosing, Grade, and Study Group – Part A, Group 1

[Implementation Note: If the number of Study Groups or assessment time points causes this table to be too wide (wider than the page), then split this table by Study Group (i.e., one table per Study Group).

If an assessment has a grading scale that includes grading for both high and low, then include one row for each severity for high and low, as shown below for Assessment 1. If not, then just include one row per severity, as shown below for Assessment 2. "Any Assessment" will just summarize one row per severity.

If there are subjects with a max severity that is both high AND low for the same parameter, then break out the "Max Severity Post Baseline" columns into a separate table.

ilu a separate taure.										
			Norn	lal	Mil	þ	Моdел	rate	Seve	re
Vital Sign Assessment	Study Day	N	u	%	u	%	u	%	u	%
Any Assessment	Baseline		х	х.х	×	х.х	x	х.х	x	х.х
	Day 28 (Visit 03)									
	Day 42 (Visit 03B)									
	Day 56 (Visit 04)									
	Day 70 (Visit 04B)									
	Day 84 (Visit 05)									
	Day 112 (Visit 06)									
	[continue for all visits with VS]									
	Max Post Baseline									
[Assessment 1]	Baseline									
	Day 28 (Visit 03)									
	Day 42 (Visit 03B)									
	Day 56 (Visit 04)									

			Norn	lal	Mil	p	Mode	rate	Seve	re
Vital Sign Assessment	Study Day	Z	u	%	u	%	u	%	u	%
	Day 70 (Visit 04B)									
	Day 84 (Visit 05)									
	Day 112 (Visit 06)									
	[continue for all visit with VS]									
	Max Post Baseline									
Assessment 2]	Baseline									
	Day 28 (Visit 03)									
	Day 42 (Visit 03B)									
	Day 56 (Visit 04)									
	Day 70 (Visit 04B)									
	Day 84 (Visit 05)									
	Day 112 (Visit 06)									
	[continue for all visits with VS]									
	Max Post Baseline									

Table with similar format:

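### The white cell shift and grade-distribution shells merge high and low grades, although WBC is graded both ways and SAP 8.6 describes low/normal/high shift tables

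*Combined protocol and SAP*

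**What the plan says.** Protocol Appendix IV has two WBC rows in its hematology table, "WBC Increase - cell/mm" and "WBC Decrease - cell/mm". Grade 1 is 10,800 to 15,000 for a rise and 2,500 to 3,500 for a fall, and each direction runs to Grade 4.

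SAP 8.6 defines two kinds of laboratory shift table. The first is Normal/Abnormal. The second is headed "For laboratory parameters with three categories: Low, Normal and High (Ordinal response", and its layout is described in these terms: "shift table displays the number of subjects who are categorized as low, normal, or high at baseline cross tabulated with low, normal or high results". A proportional-odds GEE with two intercepts, hence three ordered categories, goes with it.

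In SAP Appendix 1, the WBC tables for Part A (130 to 132), titled "Shift Table for WBC by Study Group Comparing Baseline to Post-Baseline Measures", are listed as having the same format as Table 127. That shell crosses Normal, Grade 1, 2, 3 and 4 at baseline with the same five levels after baseline. Table 111, the distribution shell for graded parameters, uses the same five columns and is copied in Tables 112 to 113 and 115 to 116.

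The implementation note to the vital-signs shell, Table 174, does call for a split: "If an assessment has a grading scale that includes grading for both high and low, then include one row for each severity", separately for high and for low. The laboratory shells carry no such note.

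**The concern.** With undirected grades, leukopenia and leukocytosis of the same grade fall in one cell. A move from one to the other is shown as no shift, and a rise in low values can be offset by a drop in high ones. The text also describes a table that no printed shell delivers.

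Safety against placebo is a primary objective of Part B, and falls in blood counts are a reasonable thing to watch. Protocol 8.6.1 gives a "temporary decrease in white blood cell count" as its example of laboratory changes in earlier DNA vaccine studies. In the Phase 1 study of the similar vaccine (VRC 319, Protocol 1.4), 14 of the 17 related unsolicited events were count decreases: neutropenia 7, lymphopenia 4, leukopenia 2, thrombocytopenia 1. A reader of the final report would want the number of subjects per arm who crossed a low WBC threshold at each visit.

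**Working it through.** **1. Text against shells**

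| Source | Categories for WBC |
|---|---|
| Appendix IV | Grades 1 to 4 high; Grades 1 to 4 low |
| SAP 8.6, item 2 | Low, Normal, High (WBC not named) |
| Tables 130 to 132 (as Table 127) | Normal, Grade 1 to 4 |
| Tables 111 to 113, 115 to 116 | Normal, Grade 1 to 4 |
| Vital signs, Table 174 | Separate high and low rows |

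WBC is the only planned laboratory parameter with both an increase row and a decrease row in Appendix IV, so it is the natural case for SAP 8.6 item 2. A five-level Normal/Grade grid cannot feed a three-category ordered model without a further rule.

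**2. One subject.** Baseline 11,000 (Grade 1 high), follow-up 3,200 (Grade 1 low). The Table 127 layout puts this subject in the Grade 1 by Grade 1 cell, on the diagonal. A low/normal/high table would show High to Low.

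**3. Visits and the adverse event window, Part B.** Schedule of Evaluations Table C has blood counts at Weeks 0, 4, 8, 16 and 44. Protocol 4.2.4 has blood drawn before product is given, so the Week 8 sample precedes dose 3. Protocol 5.1.1 closes unsolicited event recording at Visit 05 (Week 12) for subjects given three doses. After that, only serious events, new chronic conditions and dengue are recorded. No scheduled Part B count after dose 3 therefore falls inside the window. SAP 8.6 lists Week 20 where the schedule has Week 44; both are after Week 12, so the point is unchanged.

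**4. Illustration of what merging can do.** The documents give no WBC rates, so everything here is assumed.

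As an anchor, protocol Table 7 has n = 1200 per group, 1.0% against 2.50%, 80% power. With pooled rate 0.0175, the null SE is sqrt(0.0175 × 0.9825 × 2/1200) = 0.00535. The alternative SE is sqrt((0.0099 + 0.024375)/1200) = 0.00534. Power = Φ((0.015 − 1.96 × 0.00535)/0.00534) = 80.05%, which agrees.

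Now take low WBC as 1.0% on placebo and 2.5% on vaccine (12 and 30 subjects), with high WBC the mirror image (30 and 12). Merged, the table shows 42 against 42. Split, low WBC is 12 against 30 (z = 0.015/0.00535 = 2.80, p = 0.005).

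Exact cancellation is a chosen case. A less contrived version uses a lognormal WBC with the printed Grade 1 limits (3.5 and 10.8 thousand) and a 10% fall on vaccine. Low = Φ(ln(3.5/m)/s) and high = 1 − Φ(ln(10.8/m)/s), with median m (in thousands) and log-SD s.

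| Median, log-SD | Low, placebo → vaccine | Any grade, placebo → vaccine |
|---|---|---|
| 6,500, 0.28 | 1.35% → 3.33% | 4.84% → 4.76% |
| 6,000, 0.27 | 2.30% → 5.41% | 3.77% → 5.93% |
| 7,000, 0.28 | 0.67% → 1.79% | 6.74% → 4.50% |

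The merged count can cancel, dilute or reverse the change in low values. Which one happens depends on the assumed distribution. The calculation also ignores the Appendix IV rule that values inside the institutional range are not graded.

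**The case against.** The strongest reply is that direction is reported elsewhere. Tables 117 to 121 give change from baseline by arm and visit, Protocol 6.4.2 adds a 95% CI for mean change, and WBC has box plots and mean-change figures. A uniform downward shift of 0.2 SD with 1200 per arm would give z = 0.2/sqrt(2/1200) = 4.9 on the visit means, and protocol Table 8 puts the detectable shift at 0.11 SD with 80% power. A reader might infer that the by-arm laboratory tables cannot show direction, or that the plan hides a fall in white cells. The documents do not support that.

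Further points also stand:

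- SAP 8.6 reports abnormal results as adverse events. These are coded to directional terms and compared by arm, which covers the Week 4 and Week 8 counts in Part B.
- Neutrophils and lymphocytes have their own shift tables and are graded for decrease only.
- The SAP plans no test on merged grades, so power figures for such a test would not describe the plan.
- The Protocol 8.6.1 sentence covers placebo as well as vaccine recipients, so it does not make a WBC fall the expected vaccine effect.

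The reply does not remove the gap. Means and box plots do not count subjects beyond a threshold. Abnormal-result Tables 167 and 168 are limited by SAP 8.6 to subjects with at least one Grade 2 or higher result, and they are listings rather than counts by arm. The adverse event route closes before the Week 16 and Week 44 counts in Part B.

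**Conclusion.** The inconsistency is real and narrow. WBC is graded in both directions, SAP 8.6 describes low/normal/high shift tables, and the WBC shift and distribution shells have no direction. By-arm counts of low versus high WBC are therefore not available from those tables. For Part B after dose 3, they are the main by-arm count of subjects with graded WBC values. The size of any masking cannot be fixed from the documents, and the figures above are illustrations only.

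Two inferences are involved. SAP 8.6 does not name WBC; its place there follows from the two-way grading. The shells for Part B Tables 148 to 166 do not appear in the text reviewed; the format of Tables 155 to 156 is inferred from their per-group titles, which match those of the graded Part A tables.

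A reader might extend the point to parameters with decrease rows only and conclude that a high hemoglobin can only be shown as Normal. Appendix IV rules that out: hemoglobin above the upper limit of normal is an adverse event graded by the clinical illness criteria.

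**What to change.** Apply the Table 174 rule to WBC in Tables 111 to 113, 115 to 116, 130 to 132 and 155 to 156, with separate categories by severity for high and for low. Alternatively, supply the Low/Normal/High shift table that SAP 8.6 describes. Either way, name WBC in SAP 8.6 as a three-category parameter and state how directed grades collapse to the three GEE categories, so that text, model and shells agree. Tables 169 to 173 share the undirected layout and could take the same split.

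This changes shells and programming only. Hematology Listings 32 and 33 already carry each result with its reference range, so no new data are needed. The downside is wider tables.
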